11 Appendices	29

LIST OF ABBREVIATIONS

AE	Adverse Event
DSMC	Data and Safety Monitoring Committee
DSMP	Data and Safety Monitoring Plan
FDA	Food and Drug Administration
GCP	Good Clinical Practice
HPV	Human Papillomavirus
NCI	National Cancer Institute
NIH	National Institutes of Health
OHRP	Office for Human Research Protections
SAE	Serious Adverse Event

STUDY SCHEMA

[figure not shown]

Fig. 2 Design of the PRESTIS (Prospective Evaluation of Self-Testing to Increase Screening) trial

1 INTRODUCTION

1.1 Study Rationale

The PRESTIS Trial (Prospective Evaluation of Self-Testing to Increase Screening) described here is a parallel, single-blinded, three-arm RCT comparing the effectiveness of three outreach strategies for improving cervical cancer screening participation and attendance for clinical follow-up among women aged 30-65 years who are overdue for Pap test screening.

1.2 Background

The implementation of clinic-based Papanicolaou (Pap) screening for cervical cancer has dramatically reduced the incidence of this disease in the US and other countries with widespread screening programs. However, despite over \$5.4 billion spent annually on routine screening, almost 20% of US women remain at high risk for cervical cancer due to screening non-attendance (i.e., their inability or unwillingness to periodically attend for clinic-based screening according to the screening guidelines). In fact, over half of the 13,000 cases of invasive cervical cancer diagnosed in the US each year are among screening non-attendees. Cervical cancer results in over 4,000 deaths annually, and its treatment and follow-up costs total over \$440 million. While screening non-attendance is largely due to inadequate access to preventive care, multiple personal and cultural barriers also affect women's participation in timely screening. These barriers include language and cultural differences with providers, discomfort during a pelvic exam, education/literacy, and health beliefs. Our research suggests that modesty concerns and the unacceptability of a male physician may also play a role. Many of these factors continue to adversely impact screening participation after medically underserved women gain access to healthcare. While the availability of licensed vaccines to prevent infection with the etiologic agent, high-risk human papillomavirus (HR-HPV), creates new opportunities to reduce the incidence of both cervical cancer and pre-invasive cervical disease, low rates of vaccine uptake in the US means that cervical cancer risk will persist for at least several generations of women. Cost-effective strategies to improve existing screening programs thus will be required for the foreseeable future.

At present, evidence-based, client-directed strategies such as patient reminders and recalls, one-on-one patient education, and patient navigation, are the basis for behavioral interventions to increase cervical cancer screening rates. Patient reminders inform patients that they are due for screening, while recalls inform them they are past-due. Patient navigation, a barrier-focused intervention, involves individual interactions with patients to address individual-level barriers along the continuum of care through to a specific endpoint (e.g., cancer screening). These existing client-directed strategies alone are often unable to resolve many of the barriers faced by screening non-attendees. Of note, we recently found that as many as 10% of women attending safety net community health centers in Harris County reported never having had a Pap test despite having visited those clinics an average of nearly four times in the past year. This observation suggests that current standard of care cervical cancer screening may be simply unacceptable or unfeasible for many women.

Testing self-collected cervicovaginal samples for HR-HPV may be an effective strategy to overcome the multiple barriers that hinder clinic-based screening. Testing for HR-HPV has been shown to be equally or more sensitive than liquid-based cytology for detecting invasive cervical cancer and high-grade lesions. Reflecting its sensitivity, HR-HPV testing using provider-collected samples is now recommended by the US Food and Drug Administration (FDA) as an alternative to Pap test screening. Recently, it has become the primary screening tool in The Netherlands and Australia and is being considered as such in several other countries. Substantial evidence indicates that samples can be collected by providers or by women themselves, with similar sensitivity for detecting HR-HPV nucleic acid. Numerous studies, including our own, have demonstrated high acceptability for a self-sampling modality. In our own research, a sizeable

proportion of women indicated a preference to utilize self-collected samples rather than undergo a pelvic examination by a healthcare provider and considered self-sampling more convenient and less stressful than clinic-based screening. These and other data thus pave an exciting path for the expansion of primary screening from clinical settings into women's homes through mailed self-sample HPV testing kits.

Mailed self-sample HPV testing has been evaluated in multiple trials in Europe, Australia, and Canada as an additive strategy to increase primary screening participation among screening non-attendees of organized population-based screening programs. These trials have reported that as many as 10-39% of non-attendees complete and return the mailed self-sampling kits. Despite these promising results, there has only been one published trial in the US to evaluate mailed self-sample HPV testing in the analogous setting of an integrated health system, i.e., a health system that focuses on coordinated care provision across the care continuum. The HOME (Home-based Options to Make Cervical Cancer Screening Easy) trial is a pragmatic randomized controlled trial (RCT) that is being conducted within the Kaiser Permanente system, a highly organized, private health system that serves a predominantly non-minority and privately insured patient population. To date, no RCTs have been conducted in safety net healthcare systems nor in a predominantly racially/ethnically minority patient population. Evaluating mailed self-sample HPV testing in this context is important both because safety net health systems (i.e., those that offer access to care regardless of the patients' ability to pay) serve a large proportion of socioeconomically disadvantaged individuals in the US and because racial/ethnic minorities, particularly Hispanic and non-Hispanic black women, carry a disproportionate burden of cervical disease.

The PRESTIS Trial (Prospective Evaluation of Self-Testing to Increase Screening) described here is a parallel, single-blinded, three-arm RCT comparing the effectiveness of three outreach strategies for improving cervical cancer screening participation and attendance for clinical follow-up among women age 30-65 years who are overdue for Pap test screening. Being overdue for a Pap test is defined as not having a Pap test in the past 3.5 years or more, which is based on a three-year screening interval and a 6-month grace period. The study arms are: 1) telephone recall (control arm); 2) telephone recall with mailed self-sample HPV testing kit (intervention arm); and (3) telephone recall with mailed self-sample HPV testing kit and patient navigation (intervention plus arm). The primary outcome is completion of primary screening, defined as completion and return of mailed self-sample kit or completion of a clinic-based Pap test. Secondary outcomes are predictors of screening and attendance for clinical follow-up among women with a positive screening test. Additional exploratory outcomes are detection and treatment of cervical precancers and cost-effectiveness. The contribution of the PRESTIS Trial is significant because it will define how and under what conditions self-sample HPV testing can be used cost-effectively by safety net health systems for primary screening and early detection of cervical precancer among non-attendees.

Background for administrative supplement to expand enrollment to Asian/Asian American women: The patient population of the safety net health system (serving primarily low income women) where the PRESTIS trial is embedded is 67% Hispanic, 22% non-Hispanic Black, 7% non-Hispanic White, 5% Asian, and 2% other race/ethnicity. Reflecting this demographic composition and logistical constraints of implementing the trial in multiple languages, eligibility is currently limited to patients who speak English or Spanish. Asian/Asian American women who speak English currently comprise a small proportion of trial participants (4%). Furthermore, Asian/Asian American women who speak languages other than English (particularly Vietnamese, the primary language of 68% of Asian patients) are ineligible for the trial. The small number of Asian/Asian American patients in the trial is problematic as it precludes their inclusion in subgroup analyses and limits the generalizability of trial findings. The inclusion of Asian/Asian American women in self-sampling trials is particularly important given that cervical cancer screening participation is lowest among Asian/Asian American women in the U.S. (63.7% vs. 79.5% among non-Hispanic Whites (7), and certain Asian subpopulations, notably Vietnamese women, have higher cervical cancer incidence compared to women of other race/ethnicities (8, 9). With the administrative supplement, we will expand the PRESTIS trial by adapting patient

education materials and navigation strategies to recruit Asian women who are not up-to-date on their cervical cancer screening.

1.3 Describe Unmet Needs and Knowledge Gaps

To date, no RCTs have been conducted in safety net healthcare systems nor in a predominantly racially/ethnically minority patient population. Evaluating mailed self-sample HPV testing in this context is important both because safety net health systems (i.e., those that offer access to care regardless of the patients' ability to pay) serve a large proportion of socioeconomically disadvantaged individuals in the US and because racial/ethnic minorities, particularly Hispanic and non-Hispanic black women, carry a disproportionate burden of cervical disease.

1.4 Intention of Research

This research builds on prior research conducted by the PI.

2 OBJECTIVES

2.1 Primary Objectives

The overall purpose of this protocol is to evaluate the effectiveness of self-sample HPV testing with patient navigation to increase cervical cancer screening among women who otherwise do not regularly attend for clinic-based screening (i.e., Pap test).

The specific aims of this protocol are to: SPECIFIC AIM 1: Compare the effectiveness of mailed self-sample HPV testing alone and in combination with patient navigation to increase primary screening participation (primary outcome) and clinical follow-up (secondary outcome).

Hypothesis 1.1: Primary screening participation and clinical follow-up will be significantly greater among women randomized to receive telephone recall with mailed self-sampling kits versus telephone recall alone. Hypothesis 1.2: There will be significant incremental gains in screening participation and clinical follow-up among women randomized to receive mailed self-sampling kits in combination with patient navigation.

After receiving an administrative supplement, we have revised the trial to include Asian/Asian American women who are currently under-presented in the trial and in the broader literature on self-sampling. In doing so, we will ensure that the trial is powered to rigorously assess and compare screening participation and other outcomes across racial/ethnic and linguistic subpopulations inclusive of Asian/Asian American women. Collectively, the data generated in pursuit of these aims and those of the larger trial will define the impact of mailed self-sample HPV testing among medically underserved Asian/Asian American and other racial/ethnic minority women in safety net health system settings.

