3 STUDY METHODS

3.1 Study Methods

Eligible women will be identified monthly through a query of the EMR database. Data will be extracted and transferred to OnCore (Forte Research Systems, Madison, WI) for randomization, storage, and data management. A computer-generated permuted block randomization scheme will be used to randomly assign individuals to the three trial arms with a 1:1:1 ratio using participants' medical record number. Randomized women will receive a study-specific identification number. Randomized women will be contacted by telephone. Those who are not reached will be contacted on 3 different days at 3 different times before being classified as unreachable. Unreachable participants will be replaced by randomly-selecting additional eligible women until the target sample size is met. Women who hang up the telephone before the scripted message is delivered will receive a second call within 10-30 minutes. Those who do not hear the full message on the second attempt will be categorized as refusers.

The 3 arms of the RCT are: Arm 1: Telephone recall (control). Participants will receive a scripted telephone recall from a trained patient navigator (PN) on behalf of Harris Health. Arm 2: Telephone recall with mailed HPV self-sampling kit (intervention). Participants in this arm will receive a scripted telephone recall from a PN on behalf of Harris Health and receive a mailed HPV self-sampling kit with a pre-paid return envelope.

Arm 3: Telephone recall with mailed HPV self-sampling kit and patient navigation (intervention plus). Participants in this arm will receive the same scripted telephone recall and mailed self-sampling kit as in Arm 2. Within 3-5 days of the kit's mail-out, participants will receive a telephone call from the PN.

Procedures for the three arms of the RCT are as follows:

Arm 1: Telephone recall (control). Participants will receive a scripted telephone recall from a trained patient navigator (PN) on behalf of Harris Health. PNs will let the patient know of the telehealth options available to Harris Health patients during the COVID-19 pandemic. Patients will be given the contact information for the call center that can walk them through the steps of accessing telehealth. PNs will also inform participants that their records indicate that they are overdue for a Pap test and that primary care, including well woman exams and Pap testing is still important during the pandemic.

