Ascertainment of Outcomes Primary outcome. The primary outcome is primary screening participation, defined as completion and return of a mailed self-sample HPV testing kit that is tested in the lab or attendance for clinic-based screening within 6 months of randomization. Receipt of mailed self-sample HPV testing kits will be ascertained by reviewing lab records. Attendance for clinic-based screening will be ascertained by the study coordinator based on review of the Harris Health EMR. Primary screening participation will be dichotomously categorized as screened/unscreened. Secondary outcomes are screening tests results (positive, negative, or inadequate) and completion of clinical follow-up among women with an abnormal screening test result (attended, did not attend). Screening test results will be ascertained within 6 months of randomization. Pap/HR-HPV co-testing results will be ascertained by EMR review. Self-sample HR-HPV test results will be based on laboratory reports. Completion of clinical follow-up will be ascertained by EMR review within 6 months of the date of the screening test result. Completion of clinical follow-up is defined as attendance for colposcopy among participants who had a positive test by clinic-based screening and attendance for colposcopy or subsequent clinic-based screening among those who had a positive test by self-sampling. Additional exploratory outcomes (sub-aim 2) are detection and treatment of cervical precancers (i.e., histologically-confirmed cervical intraepithelial neoplasia grade II or greater [CIN2+]). Precancers will be ascertained by EMR review within 6 months of abnormal screening results and treatment as per ASCCP guidelines will be ascertained within 6 months of the date of diagnosis. Completion of primary care appointments will be ascertained at 6 months, including telehealth appointments. Additional variables will be collected to meet the aims of the NIH-funded supplement (3R01MD013715-04S1) to the parent trial: HIV status, Preventive Care Gap Score, Enrollment in MyHealth portal, History of COVID-19 diagnosis, HPV vaccination status and Risk of Admission or ED visit. We will also collect Mental and Behavioral Disorders due to use of the following: alcohol (Code F10), opioids (Code F11), cannabis (Code F12), sedatives, hypnotics, anxiolytics (Code F13), cocaine (Code F14), other stimulants, including caffeine (Code F15),

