3.4 Data Analysis

Randomized Controlled Trial Primary outcome. Primary screening participation will be examined dichotomously (screened/not screened) using an "intent-to-screen" analytic approach. Bivariable tables and Pearson's χ^2 tests will be used to compare the proportion of primary screening participation across Arms 1, 2, and 3, as well as the absolute difference in participation across Arms 1, 2 and 3. Bivariable tables and Pearson's χ^2 tests will be used to compare the proportion of primary screening participation by study arm, as well as the absolute difference in participation across arms. Log binomial regression will be used to calculate the relative risks of primary screening participation and corresponding 95% confidence intervals (CIs). Secondary outcomes. Descriptive analyses of secondary outcomes will be conducted using bivariable tables and Fisher's exact tests to describe and compare test results and attendance for clinical follow-up across study arms 1, 2 and 3. Log binomial regression will be used to calculate relative risks and 95% CIs of having a positive screening test and of attending for clinical follow-up.

Analytic sub-aim: 1) We will use descriptive statistics (bivariable tables and chi-square/Fisher's exact tests) to compare characteristics of un/under-screened women and those who are up-to-date on screening across Arms 1, 2, and 3. Multivariable logistic regression will be used to assess the independent association between screening status and participant characteristics. 2) Detection and treatment of precancers will be explored through descriptive analyses using bivariable tables and Fisher's exact tests. 3) Among participants in Arms 1, 2 and 3, we will conduct separate analyses to assess characteristics associated with primary screening participation. For Arms 1, 2 and 3, we will use bivariable tables with Pearson's χ^2 tests to describe characteristics of screened and unscreened participants. Characteristics of interest include age, race/ethnicity, months since last Pap test, health plan type, number of healthcare encounters in the past 12 months, and time enrolled as a Harris Health patient. Associations with $p<0.10$ will be used to determine candidate variables for subsequent multivariable

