4 STUDY POPULATION

Randomized Controlled Trial In a systematic review, patient navigation was associated with a 15% improvement over standard of care for completion of primary colorectal cancer screening, with the proportion of participants who complete screening after navigation ranging from 27-67%. As the degree to which HPV and colorectal screening are analogous is unknown, we chose to err on the conservative side and, in order to ensure adequate power, based our calculations on the assumption that at least a 6% difference exists between screening non-attendees who complete mailed self-sample HPV testing with patient navigation compared to those who complete the self-sample testing without patient navigation. With 756 participants in each study arm and a total of 2,268 (nQueryAdvisor version 7.0), we can expect to detect the indicated differences in proportions between Arms 2 and 3. Given the large numbers of screening non-attendees enrolled in Harris Health (>15,000), we anticipate that we will be able to accrue this number of participants over a period of 30 months, with completion of follow-up in 36 months.

The sample size has been revised to account for an additional 240 Asian/Asian American women who will be enrolled as part of an administrative supplement. For the Asian/Asian American targeted enrollment study, the estimated number of participants who can be enrolled in a six month period with the two patient navigators who will remain on the team is 240. A recent meta-analysis of trials showed a pooled 12.8% improvement in intent-to-treat analyses measuring screening uptake in mail-to-all self-sample HPV testing

compared to usual care (4). Using this data, our sample size of 240 (120 in Arm 1, 60 each in Arms 2 and 3) provides 85.2% power to detect an improvement of 12.8% between usual care (Arm 1) and mailed self-sampling (Arms 2 and 3 combined) with alpha=0.05 (30).

Telephone Survey The sample size is designed to assess the main effect of patient navigation on reported barriers to self-sampling. Specifically, it is designed to detect a 25% difference in the proportion of participants who report one of the top three barriers reported in our previous research (concerns of injury, safety, and cleanliness), comparing women who did and did not receive patient navigation. Specifying an expected proportion of 0.30, 80% power, and $\alpha=0.05$, the target sample size is 272 (n=68 in each group of the factorial design).

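### Section 2.1 says the trial is powered to compare racial/ethnic and linguistic groups, but section 4 sizes no between-group contrast, so the claim holds only in part

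*Combined protocol and SAP*

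**What the plan says.** The claim stands in section 2.1 (Primary Objectives), in the paragraph on the administrative supplement: "we will ensure that the trial is powered to rigorously assess and compare screening participation and other outcomes across racial/ethnic and linguistic subpopulations".

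Section 4 (Study Population) holds two sample size statements for the randomised trial.

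- **Main trial:** 756 women per arm and 2,268 in total, for a 6-point difference, with which "we can expect to detect the indicated differences in proportions between Arms 2 and 3".
- **Supplement:** 240 Asian/Asian American women, 120 of them in Arm 1 and "60 each in Arms 2 and 3) provides 85.2% power to detect an improvement of 12.8% between usual care (Arm 1" and Arms 2 and 3 combined, at alpha 0.05. Section 4 gives 240 as the number that two navigators can enrol in six months.

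Section 1.2 reports that "Asian/Asian American women who speak English currently comprise a small proportion of trial participants (4"%). It also gives the racial/ethnic mix of the health system, with 7% non-Hispanic White.

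In section 3.4, sub-aim 3 reads "Among participants in Arms 1, 2 and 3, we will conduct separate analyses to assess characteristics associated with primary screening participation". The variables are then listed: "Characteristics of interest include age, race/ethnicity, months since last Pap test, health plan type, number of healthcare encounters in the past 12 months"; length of enrolment in the health system completes the list. Language is not named, no arm-by-group term is described, and no between-group analysis of clinical follow-up is planned.

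Section 3.1 says that the scheme will "randomly assign individuals to the three trial arms with a 1:1:1 ratio". It defines the follow-up outcome as "completion of clinical follow-up among women with an abnormal screening test result (attended, did not attend".

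**The concern.** Power to compare outcomes across subpopulations is a statement about contrasts between groups. The 85.2% in section 4 belongs to a contrast between arms inside one group. A trial can be well sized for the second and poorly sized for the first.

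The claim also reaches beyond participation to other outcomes, and Aim 1 in the same section names clinical follow-up as the secondary outcome. That outcome exists only for women with an abnormal result, so its group counts are much smaller.

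Subgroup inference is the stated reason for the supplement. A reader who trusts section 2.1 could take the lack of a significant difference between Asian and other women in benefit or follow-up as evidence of similarity, when a sizeable partial difference would usually be missed.

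**Working it through.** **Inputs from the documents.** 2,268 women, 756 per arm (section 4). Supplement of 240, split 120/60/60, effect 12.8 points, alpha 0.05, sidedness not stated (section 4). Asian women 4% of current participants; 7% of the health system's patients non-Hispanic White (section 1.2).

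**Assumptions, because the documents give no figure.** Two-sided 0.05. Arm 1 screening rate 6.5-20%. The 4% share holds for all 2,268 and is spread evenly over arms. Overall participation in the comparison group 15-30%. Test positivity 10-25%. The halved kit effect is a yardstick chosen here, not one the plan sets.

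**1. The plan's 85.2%.** For two proportions, power = Φ[(d − 1.96·s0)/s1], with s0 = √[p̄(1−p̄)(1/n1+1/n2)] and s1 = √[p1(1−p1)/n1 + p2(1−p2)/n2]. The Arm 1 rate is not stated, so the figure cannot be reproduced from stated inputs alone. With 120 per side and an Arm 1 rate of 6.2%, s0 = 0.0429, s1 = 0.0421, and power = Φ(1.045) = 85.2%. At 10% it is 76.7% and at 20% it is 61.5%. So 85.2% is attainable two-sided at a low Arm 1 rate. It is not a between-group figure.

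**2. Group sizes.** 4% × 2,268 = 91 women, about 30 in Arm 1 and 60 in the kit arms. Added to the supplement: 331 Asian women, 150 in Arm 1 and 181 in the kit arms. Others: 2,177, about 726 and 1,452. Non-Hispanic White: 7% × 2,268 = about 159.

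**3. Participation over all arms, Asian women higher.** Example: base 30%, gap 8 points, 331 v 2,177. s0 = 0.0273, s1 = 0.0284, power = Φ[(0.080 − 0.0535)/0.0284] = 82%. Over base rates 30% to 15%:

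| Gap | 331 v 2,177 | 331 v 159 |
|---|---|---|
| 8 points | 82-94% | 41-54% |
| 10 points | 95-99% | 58-72% |

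**4. Difference in kit effect (Arm 1 v Arms 2+3), Asian v all others.** SE = √Σ p(1−p)/n over the four cells.

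- Both groups given the 12.8-point effect. Arm 1 rate 6.5%: √(0.000405+0.000861+0.000084+0.000107) = 0.038. Arm 1 rate 20%: √(0.001067+0.001218+0.000220+0.000152) = 0.052.
- Difference detectable with 80% power = 2.80 × SE = 10.7 to 14.4 points, about the size of the whole assumed effect.
- Power for 6.4 points = Φ(0.064/SE − 1.96) = 39% down to 24%. If the variance is set for a halved effect in Asian women, SE is 0.035 to 0.050 and power is 45% down to 25%. Together: 24-45%.
- Only the 240 counted as Asian (120/120 v 756/1,512): 19-35%.
- No effect at all in one group (12.8 v 0): 76-99% if that group is Asian women, 71-93% if it is the others. With only the 240, no effect in Asian women: 64-96%.

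**5. Clinical follow-up.** Asian women screened = 150 × p + 181 × (p + 0.128), which is 45 at p = 6.5% and 89 at p = 20%. At 10-25% positivity that gives about 4 to 22 positive Asian women, against 33 to 155 others. For a 20-point lower attendance in Asian women (others 40-70%), Fisher's exact test has about 1-9% power at 4 v 33 and 38-40% at 22 v 155.

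**6. Arm mix.** Share in Arm 1: Asian 150/331 = 45%, others 33%. If kit effect and Arm 1 rate were identical in both groups, pooling without arm would still show a gap of (0.453 − 0.333) × 12.8 = 1.5 points, with Asian women lower.

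**The case against.** The best defence is that section 2.1 is a forward-looking sentence and that the outcome it names first, participation, is adequately powered for gaps of 8 to 10 points between Asian and all other women. That stands. A reader might infer that the trial has no useful power for any group comparison; step 3 shows otherwise.

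Section 2.1 also does not mention differences in kit effect. That stands too: an interaction test is not something the plan promised and omitted, and the halved effect is a chosen yardstick. A reader might go further and infer that the trial could not detect any difference in kit effect. The calculations do not support that, since complete absence of effect in one group has about 71-99% power with 331 Asian women. The weakness concerns partial differences.

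The opposite overreach is equally tempting: to write into section 2.1 that large participation gaps are detectable. That fails for small groups such as about 159 non-Hispanic White women.

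Nothing in the plan says that a non-significant difference will be read as equal effect, so that harm is a risk of interpretation and not a planned step. Most inputs are assumptions, and the follow-up power range is wide. What does not depend on them is that section 4 contains no between-group calculation, which the defence does not dispute.

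**Conclusion.** The power claim in section 2.1 is wrong as written because it is broader than anything section 4 sizes. It is an overstated claim. A reader might infer an arithmetic error in the 85.2%, but that figure is attainable at an Arm 1 rate near 6.2%, and the documents give no rate that contradicts it.

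The claim holds in part for participation (Asian v all others) and fails for the smallest groups. It is weak for a partial difference in kit effect and unsupported for clinical follow-up. These conclusions hold across Arm 1 rates of 6.5-20% and both ways of counting Asian women. The follow-up counts rest further on the assumed 10-25% positivity.

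The primary between-arm analysis is untouched. I am highly confident that the calculation is absent, and less so about individual power values.

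**What to change.** (a) In section 2.1, replace the power claim with wording such as: *The supplement is sized, under stated assumptions, for Arm 1 v Arms 2+3 within Asian/Asian American women; comparisons of participation, intervention effect and clinical follow-up between racial/ethnic or language groups were not sized, are exploratory, and will be reported with 95% CIs.* Do not add a general statement that large between-group gaps can be detected.

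(b) In section 3.4, say whether the race/ethnicity analyses are run arm by arm or pooled. If pooled, include arm in the model, because the supplement's 120:60:60 split differs from the 1:1:1 ratio in section 3.1. An arm-by-group estimate with its confidence interval may be added as exploratory; from step 4 the expected half-width for Asian v other women is 1.96 × SE, about 7 to 10 points.

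Cost: one sentence in section 2.1, a line or two and one model term in section 3.4, and a less favourable power statement. Race/ethnicity is already a planned variable, and no enrolment is added.
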